#### Overall success rate at 18 months:

This endpoint will be derived as follows:

- For patients with stage 2 HAT: same algorithm as for the primary endpoint (cf. [Section 10.1](#)).
- For patients with stage 1 and Intermediate-stage HAT: same algorithm as for the secondary endpoint “Endpoint at 18 months” (cf. [Section 10.1](#)).

### 6.3. Other secondary efficacy endpoints

#### Time to proven and definitive failure in Patients with Stage 2 HAT

The starting point is administration of acoziborole. The time of failure is the time of the first objective evidence of sustainable failure defined as:

- Death for any reason (at any time on or after administration of acoziborole)
- Decision to use rescue medication (at any time on or after administration of acoziborole)
- Observation of trypanosomes in any body fluid at M6, M12 or M18
- a CSF WBC above 50 / $\mu$ L at 6 months followed by a confirmation of failure defined as:
  - CSF WBC above 20 / $\mu$ L at 12 months, and/or
  - CSF WBC above 20 / $\mu$ L at 18 months, and/or
  - Sign and symptoms evoking a relapse at M12, and/or
  - Sign and symptoms evoking a relapse at M18.
- a CSF WBC above 20 / $\mu$ L at 12 months followed by a confirmation of failure defined as:
  - CSF WBC above 20 / $\mu$ L at 18 months, or
  - Sign and symptoms evoking a relapse at M18.
- a CSF WBC above 20 / $\mu$ L at 18 months

This endpoint will be derived as follows:

- Proven and definitive failure patients:
  - Event (cf. definition above)
  - Time = Theoretical time of the follow-up visit (i.e. day 15 for EoH visit, day 91 for M3 visit, day 183 for M6 visit, day 365 for M12 visit, day 548 for M18 visit)
- Non-failure patients (i.e. proven and definitive failure free):
  - If CSF WBC > 20/ $\mu$ L at 12 months and CSF WBC < 20/ $\mu$ L at 18 months:
    - Censoring at M12 visit
    - Time = Theoretical time of M12 visit (i.e. at day 365)
  - Otherwise:
    - Censoring at the last visit free from proven and definitive failure
    - Time = Theoretical time of the follow-up visit (i.e. day 15 for EoH visit, day 91 for M3 visit, day 183 for M6 visit, day 365 for M12 visit, day 548 for M18 visit)

Note: Unlike the preceding endpoints, a patient cannot be a proven and definitive failure at a given time point and a success at a subsequent endpoint. Consequently, a patient with a CSF WBC above 20/ $\mu$ L at 12 months and below 20/ $\mu$ L at 18 months will be censored at 12 months. A patient lost to follow-up is a patient censored at the last available visit if there is no evidence of failure up to the last available visit. A success at 18 months (last assessment) is a patient censored at 18 months, i.e. with no evidence of failure up to 18 months.

## 6.4. Safety endpoints

### 6.4.1. Adverse events

The following AE categories will be studied:

- All AEs collected during the study
- All AEs occurring before the intake of the study drug (i.e. from D-15 to D-1)
- Treatment-emergent adverse events (TEAE) occurring:
  - During the follow-up period (i.e. from D1 to 18 months)
  - The day of the intake of the study drug (i.e. D1)
  - During the hospitalization period (i.e. from D2 to D15)
  - Post-hospitalization period (i.e. from D16 to 18 months)
- Mild/moderate TEAE (grade 1, grade 2, mild or moderate)
- Severe TEAE (grade 3, grade 4, grade 5 or severe)
- Drug-related TEAE occurring:
  - During the follow-up period (i.e. from D1 to 18 months)
  - The day of the intake of the study drug (i.e. D1)
  - During the hospitalization period (i.e. from D2 to D15)
  - Post-hospitalization period (i.e. from D16 to 18 months)
- Serious TEAE
- Serious drug-related TEAE
- TEAE of interest

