### **2.2.3. Secondary Endpoints - Safety**

The secondary endpoints concerning the safety of acoziborole are as follows:

- Occurrence of any AE, including an abnormal laboratory test result, during the observation period. AEs will be graded according to the Common Toxicity Criteria for Adverse Events (CTCAE) of the National Cancer Institute (NCI), version 4.03 (16).
- Occurrence of any SAE during the observation period and until the end of follow-up (18 months).

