#### 6.4.4. At Unscheduled Visits

If a relapse of HAT is suspected on the basis of physical examination findings or CSF WBC at any visit, the patient must attend a return visit within 1 to 3 months, at the discretion of the Investigator.

The patient must also return to the investigational centre if s/he does not feel well, even if there is no apparent relationship with treatment or HAT.

The following assessments will be performed:

- Karnofsky performance status;
- Height, weight and BMI;
- Vital signs: body temperature, blood pressure, heart rate, respiratory rate and general status;
- Physical and neurological examinations (including signs and symptoms of HAT since the previous visit);
- Investigation of any concomitant condition that may have led to the visit;
- Testing for *T.b. gambiense* in blood and lymph, if indicated;
- CSF sampling, only if symptoms suggesting relapse are present;
- Laboratory safety assessments at the discretion of the Investigator (see Appendix 3 – Laboratory Tests; p84) – if possible, samples will be collected in the morning from patients in the fasting state:

- Haemoglobin
- Haematology: WBC, platelet count
- Biochemistry: albumin, ALP, ALT, AST, BUN, chloride, creatinine, glucose, potassium, sodium, calcium, total bilirubin, bicarbonates and total protein;
- Thyroid function test, if indicated: TSH, free T3, free T4;
- Additional safety assessments, e.g. ECG or urine analysis, may be performed at the discretion of the Investigator;
- Urine pregnancy test for women of child-bearing potential, at the discretion of the Investigator;
- Collection of concomitant medication and adverse events.

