### 6.5.4. AE Collection Period

The periods for the collection of AEs that occur in the context of the study are defined as follows:

- For **any AE** that is not considered to be an SAE: from the time of

administration of the IP on Day 1 until the 6-month follow-up visit;

- For **any SAE**: from the time of enrolment of the patient in the study (after signature of informed consent form) and **until the end of follow-up** (18 months). SAEs will be followed and analysed up to 18 months.

AEs considered to be possibly related to study participation that occur during the screening period, i.e. after signature of the informed consent form and before administration of the IP, will also be collected by the medical personnel and recorded in the CRF.

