### **7. Study Duration**

The duration of the enrolment period is estimated to be approximately 28 months.

Each patient’s participation in the study will last approximately 18 months and will include:

- pre-treatment period (pre-screening and screening, treatment of concurrent diseases) up to 15 days;
- a treatment period of 1 day;

- an observation period in hospital of a total of 15 days, including the treatment day (Day 1);
- an out-patient follow-up period of 18 months with visits at 3, 6, 12 and 18 months.

The total duration of the study is estimated to be 46 months.

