#### Definition of TEAE of interest:

If data allow, categories of adverse event of interest may be defined during the data review meeting.

Notes: Any adverse event having been reported during the study for a given patient will be classified by preferred term and corresponding system organ class using the Medical Dictionary for Regulatory Activities (MedDRA) terminology (last available version at the beginning of the coding).

AEs will be graded according to the Common Toxicity Criteria for Adverse Events (CTCAE) of the National Cancer Institute (NCI), version 4.03 (cf. Protocol reference 15)

As per protocol, serious and non-serious adverse events are collected until M6. Only SAE are collected after M6.

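### The SAP's adverse event windows never produce the protocol's D1-D15 any-AE endpoint, and its 18-month windows for all and drug-related TEAEs run past the M6 end of non-serious collection

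*SAP*

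**What the plan says.** **Endpoint.** Protocol 2.2.3 defines the first safety endpoint as "Occurrence of any AE, including an abnormal laboratory test result, during the observation period". The second is "Occurrence of any SAE during the observation period and until the end of follow-up (18 months". Only the serious endpoint is extended to 18 months, so the observation period cannot mean the whole follow-up. Protocol Section 7 fixes it as "an observation period in hospital of a total of 15 days, including the treatment day (Day 1". Protocol 6.5.3 equates the hospitalisation period with Day 1 to Day 15, and SAP 7.5 repeats D1 to D15 as the hospital observation period.

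**Collection.** Under protocol 6.5.4, events that are not serious are collected from "administration of the IP on Day 1 until the 6-month follow-up visit", and serious events to 18 months. The notes at the end of SAP 6.4.1 acknowledge this: "Only SAE are collected after M6".

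**Analysis windows.** SAP 6.4.1 sets four windows for TEAEs and the same four for drug-related TEAEs: D1 to 18 months; D1 alone; "During the hospitalization period (i.e. from D2 to D15"; and "Post-hospitalization period (i.e. from D16 to 18 months".

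**Outputs.** The overall summary in SAP 8.8.1 (patients, percentage, 95% CI) covers the 18-month period only. The by-period tables in SAP 9.1.6 (14.3.1.3 to 14.3.1.7) keep D1, hospitalization and post-hospitalization apart, and no CI is specified for them. SAP Section 11 declares a change in how repeated events are counted, but no change of window.

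**The concern.** Two separate mismatches arise.

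First, the protocol's own any-AE endpoint has no table. The SAP uses the name of the hospital period for an interval that leaves out the dosing day. The same definition carries into listing 16.2.8, where the drug-related events listed for the hospitalization period would omit D1, the day of a single-dose treatment. The split is also fragile. SAP 7.6.3 sets a completely missing onset date to the dosing date and does not let a partly missing one fall before it, so events from D2-D15 can be moved to D1.

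Second, the any-TEAE, mild/moderate, severe and drug-related rows join an interval in which every event is collected (to M6) to one in which only serious events are. A reader of the table would take the percentage as an 18-month incidence.

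Protocol 2.1.3 lists as secondary objectives the safety profile with historical NECT as a yardstick and its comparability with historical pentamidine. A figure set beside history needs a period that is stated correctly.

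**Working it through.** The documents give no adverse event rate, so there is no planned figure to reproduce. The check sets the windows side by side and then does simple arithmetic.

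**1. Windows**

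| Source | Non-serious or any AE | Serious AE |
|---|---|---|
| Protocol 2.2.3 with Section 7 (endpoint) | D1-D15 | to 18 months |
| Protocol 6.5.4 (collection after dosing) | D1 to M6 visit | to 18 months |
| SAP 8.8.1 overall summary | D1 to 18 months | D1 to 18 months |
| SAP 9.1.6 by-period tables | D1; D2-D15; D16 to 18 months | same |

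No SAP row equals D1-D15. For serious events the SAP's 18-month limit agrees with both protocol rows.

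**2. What the two hospital tables can give**

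Event counts add across the D1 and D2-D15 tables. Patient counts do not, because a patient with events in both appears twice. If p1 is the D1 incidence and p2 the D2-D15 incidence, the D1-D15 incidence p satisfies

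max(p1, p2) ≤ p ≤ min(1, p1 + p2).

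All inputs here are assumed. With p1 = 20% and p2 = 40%, p is between 40% and 60%. For N = 162 + 50 = 212 (the planned numbers):

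| p1 | p2 | Range for p | Patients |
|---|---|---|---|
| 5% | 30% | 30% to 35% | 64 to 74 |
| 10% | 40% | 40% to 50% | 85 to 106 |
| 20% | 50% | 50% to 70% | 106 to 148 |
| 30% | 60% | 60% to 90% | 127 to 191 |

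**3. How much of the labelled period has non-serious collection**

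SAP 6.3 gives nominal visit days: M6 = day 183, M18 = day 548.

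- D1 to 18 months: 183/548 = 33.4% covered; 365/548 = 66.6% not.
- D16 to 18 months: (183 − 15)/(548 − 15) = 168/533 = 31.5% covered; 365/533 = 68.5% not.

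**4. Direction and possible size**

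Let h be the in-hospital incidence and f the incidence from D16 to M6 among the rest. If no non-serious event after M6 is recorded, the table shows 1 − (1 − h)(1 − f). If the D16-M6 rate stayed constant to M18, the full 18-month figure would be 1 − (1 − h)(1 − f)^(533/168).

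| h (assumed) | f (assumed) | Shown as 18 months | Full 18 months, constant rate | Gap |
|---|---|---|---|---|
| 30% | 10% | 37.0% | 49.9% | 12.9 points |
| 50% | 20% | 60.0% | 75.4% | 15.4 points |
| 60% | 40% | 76.0% | 92.1% | 16.1 points |

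If no new patient would have had an event after M6, the gap is zero. In every row the figure shown exceeds h.

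**The case against.** The best case for the SAP has five parts.

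- **The M6 limit is disclosed.** This is true: the SAP states it in the same section that sets the windows. The collection gap was not overlooked. But the note does not reach the summary table template (SAP 9.2.23), and the windows still run to 18 months.
- **Protocol 9.7 does not restrict the any-AE percentage to D1-D15.** Also true, so an 18-month summary does not contradict that section. The mismatch is with the endpoint as worded in 2.2.3, and the protocol itself is not uniform. This softens the complaint about Section 11 but does not supply the missing output.
- **D1-D15 can be obtained from planned data.** It can: all events are listed and event counts add. The defect lies in the planned tables and their labels, not in the data.
- **Serious events are handled correctly.** They are.
- **A constant event rate after M6 has no support in the documents.** This stands. The treatment is a single dose, and events are sought daily in hospital but only at spaced visits afterwards, so early clustering is plausible. The gaps above are illustrations, with zero as the lower limit.

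Two stronger readings are tempting. A reader might infer that the 18-month figures understate the in-hospital incidence. They cannot, since a cumulative figure from D1 contains every D1-D15 event. A reader might also infer that non-serious events after M6 are counted selectively, in patients who return unwell, because the unscheduled-visit list in protocol 6.4.4 includes "Collection of concomitant medication and adverse events" with no time limit. That list is a general checklist. Protocol 6.5.4, footnote 5 to the schedule of events (Table 6) and the SAP note all end non-serious collection at M6, so the documents do not support selective counting as planned practice.

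**Conclusion.** The point holds as a fault in window definitions and planned outputs. Followed as written, the SAP does not produce the protocol's any-AE endpoint at patient level; the two hospital tables only bound it, by 5 to 30 percentage points in the assumed cases tabulated. The all-TEAE, mild/moderate, severe and drug-related figures labelled 18 months rest on non-serious collection over about one third of that period and should not be read as 18-month incidences of all such events. How far they fall short cannot be known from the documents: from nothing to about 13 to 16 points under the assumed rates.

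The coverage fractions use nominal visit days. The acceptable leeway for the M6 visit in protocol Table 2 is 5 to 9 months, so individual coverage will vary. Serious and serious drug-related outputs are sound.

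**What to change.** Amend SAP 6.4.1, 8.8.1 and 9.1.6 as follows.

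1. Add a D1-D15 table of patients with at least one TEAE and with at least one drug-related TEAE, each with a 95% CI, named as the output for protocol endpoint 2.2.3. Make listing 16.2.8 include D1. State that the cut is at study day 15, because protocol Table 2 lets the end-of-hospitalisation visit fall between D13 and D18.
2. Split the post-hospitalization period in two: D16 to the M6 visit for all TEAEs, and after the M6 visit to M18 for serious TEAEs only. Cut at each patient's actual M6 visit, with a stated rule for patients who missed it.
3. Present the any-TEAE, mild/moderate, severe and drug-related summary rows for D1 to M6. Keep the serious and serious drug-related rows to 18 months. Show serious events after M6 that are severe or drug-related in the after-M6 serious table. A plain cut at M6 would otherwise drop from those rows events, deaths among them, that protocol 6.5.4 collects and analyses to 18 months. List separately any non-serious event recorded after M6.
4. Declare the windows in SAP Section 11 and footnote the tables with the M6 limit.

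The cost is SAP wording, one new table and some re-cut ones. No new data are needed.

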#### Definition of treatment-emergent AEs:

Treatment-emergent AEs are defined as any AE which occurs on or after the date of study-drug administration or which worsen in intensity on or after the date of study-drug administration.

#### Definition of TEAE of interest:

If data allow, categories of adverse event of interest may be defined during the data review meeting.

Notes: Any adverse event having been reported during the study for a given patient will be classified by preferred term and corresponding system organ class using the Medical Dictionary for Regulatory Activities (MedDRA) terminology (last available version at the beginning of the coding).

AEs will be graded according to the Common Toxicity Criteria for Adverse Events (CTCAE) of the National Cancer Institute (NCI), version 4.03 (cf. Protocol reference 15)

As per protocol, serious and non-serious adverse events are collected until M6. Only SAE are collected after M6.

### 6.4.2. Pharmacokinetics

Concentrations of acoziborole in whole blood and CSF, and population PK parameters, i.e. clearance, AUC and half-life. Statistical analyses of the PK parameters will be performed by [REDACTED]. A separate statistical analysis plan will be prepared by [REDACTED] for these analyses.

### 6.4.3. Electrocardiogram

ECG tracings will be recorded at various time points to assess the QT/QTcF interval and variations over time. Statistical analyses of the ECG will be performed by [REDACTED]. A separate statistical analysis plan will be prepared by [REDACTED] for these analyses.

### 6.5.2. Medical history

Medical and surgical history will be coded using MedDRA dictionary (last available version at the beginning of the coding).

|                        |   |              |
|------------------------|---|--------------|
| DNDi-OXA-02-HAT (DNDi) | Statistical Analysis Plan
Version 4.0 – 17/03/2021 | Page 16 / 79 |
|------------------------|---|--------------|

#### **6.5.3. Prior and concomitant therapies**

Prior and concomitant therapies will be coded with WHO-Drug Dictionary September 2013 C-format.

- Prior therapies are therapies which stopped before the study drug administration.
- Concomitant therapies are therapies which ended on or after the study drug administration or are ongoing at the end of the trial.

#### **6.5.4. Laboratory examination**

All laboratory parameters recorded in the CRF forms “Hematology”, “Biochemistry” and “Thyroid hormones” will be used. For continuous data, the absolute change from baseline to each time point will be derived. In addition, continuous laboratory values will be compared to their reference ranges and classified as “<LLN”, “Normal” and “>ULN” at baseline and each time point.

#### **6.5.5. Extent of exposure and treatment compliance**

Extent of exposure is not applicable as dosing regimen is 960 mg (3 tablets) in a single intake on Day 1. Treatment compliance will be assessed using the number of tablets administered (0, 1, 2, 3) on Day 1. The number of re-administered tablets will be described.

## 7. DATA ANALYSIS CONSIDERATIONS

### 7.1. Statistical software

The statistical analysis will be performed using SAS® software v9.4 (or a later version).

### 7.2. Type I error

For all analyses, the type I error ( $\alpha$ ) is set to 0.05, two sided.

### 7.3. Centre effect

#### For the primary endpoint:

The primary analysis **will not be stratified by centre** because the weight of each centre in the overall population is unknown. Nevertheless, the results by centre for each cohort will be presented and a test of homogeneity (a likelihood-ratio test) will be performed on the success rates. In addition, a Forest plot will be presented to assess whether the heterogeneity is quantitative (dispersion around a central value) or qualitative (presence of very atypical centres).

#### For the overall success rate:

A centre effect is possible. In this case, an estimate of the overall success rate will also be provided, giving equal weight to each centre rather than weighting the centres based on the number of treated patients. The estimate of the rate will be given by  $p = \sum W_h p_h$  where  $W_h$  is the weight of each centre, i.e. the inverse of the number ( $h$ ) of centres ( $1/h$ ). The variance of the estimator will be equal to  $\text{Var}(P_h) = \sum W_h^2 \cdot p_h(1-p_h) / n_h$  where  $n_h$  is the number of patients in centre  $h$ .

#### Grouping of centers:

The following rules for grouping small centers will be applied for both analyses described above. If any, small centres (i.e. with less than 5 patients) within the same country will be pooled together to form one centre of size comparable to that of other centres. [REDACTED]

[REDACTED]

### 7.4. Descriptive analyses of quantitative and qualitative variables

Quantitative variables will be described by: N (number of patients with non-missing data), mean, standard deviation (SD), minimum, maximum, median, first quartile (Q1) and third quartile (Q3).

Categorical variables will be described by frequency and percentage of patients in each category. Percentages will be expressed with one decimal place. Jeffrey 95% CI interval will be provided for the primary endpoint (at M18) and secondary endpoint at M12. For other endpoints and variables, 95% CI will be computed using Clopper-Pearson exact method, if required.

## 7.5. Definition of baseline, time-windows and analysis periods

### Baseline:

For vital signs, biochemistry, haematology and thyroid parameters, baseline is defined as the last available value collected before study drug administration.

**Note:** in this trial, re-test values (if any) are collected in the CRF as 'unscheduled visits'. Re-test values are taken into account in baseline calculation.

### Analysis periods:

Study procedures will be performed in accordance with the following schedule:

- D-15 to D-1: pre-screening, screening and baseline assessment
- D1: treatment day\*
- D1 to D15: observation period at hospital
- D11: initial assessment of treatment effect (lumbar puncture)
- D15: end-of-hospitalisation (EoH) visit

Out-patient follow-up visits at 3 months, 6 months, 12 months and 18 months. The timing of follow-up visits is calculated from D1.

(\*) Please note there is no visit 'Day 0' is in this trial.

### Time-windows:

The following time-windows will be used for statistical analysis. They are defined according to time midpoint between each theoretical visit time. If 2 visits (scheduled and/or unscheduled) falls into the same time-windows, the following rules will be applied for the analysis: the **latest** visit within the corresponding time-windows will be used for the analysis.

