**Table 3 : Time-window for statistical analysis**

| Visit          | Theoretical time    | Time-window |             |
|----------------|---------------------|-------------|-------------|
|                |                     | Lower limit | Upper limit |
| Administration | D1                  | D1          | D1          |
| EoH            | Between D13 and D18 | D2          | D18         |
| 3 months       | D91                 | D19         | D136        |
| 6 months       | D183                | D137        | D273        |
| 12 months      | D365                | D274        | D456        |
| 18 months      | D548                | D457        | D639        |

Note: time-windows described in section 6.1 of the protocol were defined for operational and monitoring activities. They will not be used for statistical analysis.

Note: Time-windows will be applied and calculated visits will be used for the analysis of the following data:

- Vital signs
- Clinical signs and symptoms of HAT
- Physical examination
- Neurological examination
- HAT diagnosis (i.e. examination of blood, lymph and CSF samples)
- Laboratory examination

Time-windows will not be used for calculation of the primary endpoint and secondary endpoints since it is included in the algorithms presented in Sections 10.1 to 10.3. Time-windows will not be used for calculation of the time to proven and definitive failure endpoint since it is included in the algorithm presented in Section 6.3.

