**Shift tables according to lower and upper limits of normal range:**

For all laboratory parameters (except ASAT, ALAT and TSH), shift tables according to lower and upper limits of normal range (<LLN, Normal, >ULN) between baseline and each time point (i.e. D5, D11, M3, M6, M12, M18) for each laboratory parameters will be provided by cohort, by stage of disease and overall. On exploratory purpose, Bowker's symmetry test will be performed.

The same analysis will be provided for ASAT and ALAT using the following classes: <0.5\*LLN, [0.5\*LLN to <LLN, Normal, >ULN to 2\*ULN], >2\*ULN to 3\*ULN], >3\*ULN).

The same analysis will be provided for TSH using the following classes: <0.5\*LLN, [0.5\*LLN to <LLN, Normal, >ULN to 2\*ULN], >2\*ULN).

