**Scatterplots:**

Scatterplots between baseline value and value at each of the following time point: D5, D11, M3, M18 for the following laboratory parameters: ASAT, ALAT, Potassium, Bicarbonates, Albumin and TSH will be provided by cohort.

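### SAP 7.5 has one in-hospital window (D2-D18) and keeps only its latest visit, which contradicts the planned D5, D11 and D15 outputs and lets retests replace scheduled values

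*SAP*

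**What the plan says.** **The rule (SAP 7.5).** On how the windows were set: "They are defined according to time midpoint between each theoretical visit time". If two visits fall in one window, whether scheduled or not, the latest "visit within the corresponding time-windows will be used for the analysis". The EoH row of Table 3 gives theoretical time, lower limit and upper limit as "Between D13 and D18 | D2 | D18"; the next window (3 months) starts at D19. The scope is stated as "Time-windows will be applied and calculated visits will be used for the analysis of the following data", followed by vital signs, HAT signs and symptoms, physical and neurological examination, HAT diagnosis and laboratory examination. The protocol's visit windows are set aside for statistical analysis. Efficacy is exempt: "Time-windows will not be used for calculation of the primary endpoint and secondary endpoints", and a separate sentence exempts time to failure.

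**Retests.** Section 7.5 says that retests are recorded as unscheduled visits. Section 8.10 says that unscheduled visits enter the calculated visits and are also listed.

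**The outputs.** SAP 8.8.2 plans laboratory shift tables "between baseline and each time point (i.e. D5, D11, M3, M6, M12, M18) for each laboratory parameters will be provided" and "Scatterplots between baseline value and value at each of the following time point: D5, D11, M3, M18". Section 9.1.8 lists vital signs, HAT signs and examinations at D5, D11 and D15, and HAT diagnosis at D11. The laboratory and body-weight templates in 9.2 carry separate D5, D11 and D15 entries.

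**The concern.** The two parts of the SAP cannot both be followed. The windowing rule leaves one post-dose in-hospital record per patient, labelled EoH, while the output list asks for two or three. A programmer would have to choose which part to ignore, and the SAP does not say which.

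D5 and D11 are the only in-hospital days after dosing for which Protocol 6.3.1 schedules haematology and biochemistry. In a single-arm study with safety among its objectives, these tables are the main summary of early laboratory change.

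The same rule acts after discharge. A retest prompted by an abnormal scheduled value, if it falls in the same window, becomes the value that is analysed. The shift table then shows the retest and not the finding that led to it.

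**Working it through.** **1. Reproducing Table 3.** The theoretical days are D1, EoH (D13 to D18, nominally D15), D91, D183, D365 and D548. Midpoint = (earlier day + later day) / 2.

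| Boundary | Midpoint | Table 3 |
|---|---|---|
| M3/M6 | (91 + 183)/2 = 137 | D136 / D137 |
| M6/M12 | (183 + 365)/2 = 274 | D273 / D274 |
| M12/M18 | (365 + 548)/2 = 456.5 | D456 / D457 |
| M18 upper limit | 548 + (548 - 365)/2 = 639.5 | D639 |
| D1/EoH | (1 + 13)/2 = 7; (1 + 15)/2 = 8; (1 + 18)/2 = 9.5 | D1 / D2 |
| EoH/M3 | (13 + 91)/2 = 52; (15 + 91)/2 = 53; (18 + 91)/2 = 54.5 | D18 / D19 |

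The late limits follow the stated midpoint rule. The two early limits do not, whichever EoH day is used.

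**2. Placing the in-hospital visits.** D5, D11 and D15 all lie between D2 and D18, so all three map to EoH. No day maps to a D5 or D11 label.

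**3. Which value survives.**
- Vital signs and examinations (D5, D11 and D15 under Protocol 6.3.5 to 6.3.7): D15 is kept, and D5 and D11 are displaced.
- Haematology and biochemistry (D5 and D11 under Protocol 6.3.1; none listed for D15 in 6.3.7): if the latest value is taken, D11 displaces D5 and is labelled EoH. If the latest visit is taken, D15 is selected and the laboratory value is missing. The SAP does not say which is meant.
- Thyroid tests: D11 is the only scheduled in-hospital post-dose sample, so no D5 value exists to be displaced. D11 still has no D11 label.

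**4. Patients affected.** The plan is 155 + 7 = 162 late-stage patients and about 50 others, so about 212. Any of them with both a D5 and a D11 result is affected.

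**5. Illustration (assumed patient, not trial data).** ALT is 3.5 x ULN at D5, 1.8 at D11 and 3.2 at D91, with a retest of 0.9 at D120. D91 and D120 both fall in the M3 window (D19-D136). The windowed tables show EoH = 1.8 (or missing) and M3 = 0.9. Both values above 3 x ULN are absent from them.

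**6. The SAP's own rule with the three visits separated.** The midpoints are (1 + 5)/2 = 3, (5 + 11)/2 = 8, (11 + 15)/2 = 13 and (15 + 91)/2 = 53. Table 3 gives a whole-day midpoint to the later window (137 to M6, 274 to M12). The internal cuts are therefore D7/D8 and D12/D13.

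**The case against.** The strongest reply is that the intention is plain. Section 8.8.2, the output lists and the templates all treat D5, D11 and D15 as separate time points, and a sensible programmer would use nominal in-hospital visits. The data will exist, so the tables can be made. That stands against a reader inferring that the D5 and D11 tables are impossible: they are impossible only under the rule as written. It does not remove the contradiction. Section 7.5 applies the windows to exactly these data with no in-hospital exception, and section 11 on changes from the protocol does not mention it.

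A reader might also infer that abnormality rates will be biased downward. The retest mechanism makes this plausible, but the documents do not establish it. Protocol 1.6 gives a half-life of about 400 hours, so a D11 value may be worse than a D5 value. Protocol 6.4.4 brings back patients who feel unwell, so an abnormal unscheduled value may replace a normal scheduled one. No retest frequency is given.

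Nor are results lost. Individual and unscheduled values are listed. Under Protocol 6.5.1, clinically significant haematology or biochemistry abnormalities above CTCAE grade 1 that appear or worsen after dosing are generally reported as adverse events. Under 6.5.2, ALT or AST above 3 ULN with bilirubin above 2 ULN is an SAE. These safeguards stand, with one limit: under 6.5.4, non-serious events are collected only to the 6-month visit, whereas laboratory tests continue to 18 months.

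Latest-in-window is a legitimate prespecified convention, and nothing in the documents obliges a worst-value table. But section 8.8.2 has no other summary that would show a transient abnormality.

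**Conclusion.** The point holds as a contradiction within the SAP. Under section 7.5 as written, no D5 or D11 calculated visit exists, yet sections 8.8.2, 9.1.7 and 9.1.8 require outputs for those days. Applied literally and read per value, the rule takes D5 haematology and biochemistry out of the by-visit summaries for nearly every treated patient, and likewise D5 and D11 vital signs and examinations. This assumes near-complete attendance during the hospital stay.

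The retest effect is also real, but limited to windowed summaries and to retests in the same window as the value they follow. Its size and net direction cannot be derived from the documents.

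The primary, secondary and time-to-failure endpoints are untouched, and the D11 outcome used for futility has its own derivation (SAP 8.7, Table 5). This should be corrected to make the safety tables reproducible. It does not threaten the efficacy conclusion.

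**What to change.** - **In-hospital visits.** State in section 7.5 that D5, D11 and D15 are analysed by nominal visit. Alternatively, give each its own window, for example D5 = D2-D7, D11 = D8-D12 and EoH = D13-D18. The internal cuts follow the SAP's midpoint rule, and the outer limits are those already in Table 3. D13 must stay with EoH, because Table 3 and Protocol Table 2 allow that visit from D13. Also amend the midpoint sentence to say that the D2 and D18 limits are exceptions to it.
- **Within a window.** Give the scheduled value priority over unscheduled retests, and say whether selection is per value or per visit.
- **Transient abnormalities.** Add to section 8.8.2 a shift table from baseline to worst post-baseline value for the laboratory parameters, including unscheduled values.

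The cost is SAP wording and a little programming. No new data are needed.
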